Persistent postoperative pain and joint stiffness after total knee arthroplasty performed for osteoarthritis (Pain and Stiffness)

FUNDER: Department of Anesthesiology

PROTOCOL NO.: 2015-361

VERSION & DATE: 11/27/2019

[figure not shown]

TABLE OF CONTENTS

TAE	BLE OF CONTENTS	2
PRO	TOCOL SYNOPSIS	3
1.0	INTRODUCTION	6
2.0	OBJECTIVE(S) OF CLINICAL STUDY	9
3.0	STUDY HYPOTHESES	9
4.0	STUDY DESIGN	10
4.1 4.1.1 4.1.2	Endpoints Primary Endpoint	10 10
4.2	Study Sites	11
5.0	STUDY POPULATION	11
5.1 5.2 5.3	Number of Subjects Inclusion Criteria Exclusion Criteria	11
6.0	PROCEDURES	12
6.1 6.2 6.3 7.0	Intraoperative Protocol Postoperative Protocol Data Collection STATISTICAL ANALYSIS	15 16
8.0	ADVERSE EVENT ASSESSMENT	

PROTOCOL SYNOPSIS

Protocol Title:	Persistent postoperative pain and joint stiffness after total knee arthroplasty performed for osteoarthritis (Pain and Stiffness)
Protocol Number:	2015_361
Protocol Date:	11/27/2019
Sponsor:	Department of Anesthesiology
Principal Investigator:	[name] PhD
Objective:	 Determine if there is an association between preoperative joint fluid TNF-alpha, cytokine, chemokine, and adipokine levels and development of persistent postoperative pain and/or joint stiffness after TKA. Determine if there is an association between preoperative plasma TNF-alpha, cytokine, chemokine, and adipokine levels and development of persistent postoperative pain and/or joint stiffness after TKA. Determine the incidence, characteristics, and kinetics of persistent postoperative pain after TKA. Determine the incidence, characteristics, and kinetics of postoperative joint stiffness after TKA. Collect and store blood, joint fluid, and joint tissue for exploration of inflammatory signatures (identified by protein analyses, immunohistochemistry, RNA analysis including nanostring and sequencing analysis [RNAseq] and/or cellular analysis including flow cytometry and mass cytometry [cytoF]) associated with and potentially contributing to development of persistent postoperative pain and/or joint stiffness after TKA. Collect clinical data for examination of interactions between demographic factors, comorbidities, pre- and post-operative pain, joint stiffness, inflammatory profiles, postoperative attainment of physical therapy (PT) goals, and functional outcomes after TKA.
Study Design:	Prospective cohort study
Enrollment:	179
Subject Criteria:	Elective primary unilateral total knee arthroplasty OA with radiologic evidence of "severe narrowing" and/or "bone to bone" in the affected joint

- 3. Patients of surgeons who have agreed to participate in the study
- 4. Age > 18 years
- 5. American society of Anesthesiologists (ASA) physical status 1-3
- 6. Regional Anesthesia
- 7. Epidural PCA for postoperative pain
- 8. Adductor canal block for postoperative pain

Data Collection:

Sources: EPIC, Medical Records, and Patient Reported.

Variables: Name, MRN, Age, Race, Ethnicity, Gender, Height, Weight, BMI, Telephone number, Email address, Knee extension (degrees), Knee flexion (degrees), History of depression, history of anxiety, history of diabetes, history hyperlipidemia, history of tobacco use, Widespread pain inventory. Average daily opioid and non-opioid pain medication consumption, duration of preoperative opioid use, Most recent intra-articular steroid injection in affected joint, Statin use, gabapentinoid use, anticonvulsant use, SSRI use, Tricyclic antidepressant use, SNRI use, Presence of osteophytes on Xray, NRS pain score in operative knee at rest, NRS pain score in operative knee with movement, worst NRS pain score in operative knee in past 24 hours, least NRS pain score in operative knee in past 24 hours, PCS Questionnaire, PainDETECT Questionnaire, KOOS Knee Survey, Stiffness Questionnaire, Pain Questionnaire, Quality of life Questionnaire, KOOS Physical Function Shortform, Tourniquet time in OR, Surgery start time, Surgery end time, Length of Surgery, Surgeon, Anesthesiologist, ASA, Blood Draw completed (Y/N), Blood Draw arterial or venous (Y/N), Blood draw from side with IV (Y/N), Plasma aliquoted and stored (Y/N), Blood hemolyzed (Y/N), Joint fluid aspirated (Y/N), Did the joint fluid contain blood (Y/N), Was midazolam administered (Y/N), Joint fluid aliquoted and stored (Y/N), Was propofol administered (Y/N), was 4mg dexamethasone administered intravenously (Y/N), was fentanyl administered(Y/N), Was ketorolac administered (Y/N), was ketamine administered (Y/N), was dexmedetomide administered (Y/N), Did the patient receive neuraxial anesthesia with an epidural for postoperative pain? (Y/N), Did a patient receive an adductor canal/subsartorial saphenous nerve block containing ONLY local anesthetics (no additives)? (Y/N), Was topical TXA administered? (Y/N; dose), Was IV TXA administered either intraoperatively or postoperatively? (Y/N; dose), Changes from default TKA postop protocol? (Y/N), Was there escalation from the postoperative pain protocol at any point during the inpatient stay? (Protocol: PCEA with standard settings, oxycodone or hydrocodone 510 mg q4h prn, PO or IV acetaminophen standing dose or prn, meloxicam. E.g., needing higher doses, needing extra days of PCEA, addition of a new class of medication such as gabapentinoids, etc.) (Y/N), Epidural PCA

	Placement Time, Epidural PCA Removal Time, Time Epidural PCA Was in Place, Did the patient require IV PCA? (Y/N), Time to ambulation of 40 feet (with or without assistance), Time to independent transfer (sitstand), Postoperative joint stiffness? (Y/N), Was manipulation performed for joint stiffness?, Postoperative persistent pain? (Y/N).	
Statistical Analysis:	 Proposed analysis (e.g., student's ttest, ANOVA, chisquare, regression, etc.): Firth's penalized likelihood logistic regression Alpha level: 0.05 	
	Beta or Power level: 0.8	
	 Primary outcome variable estimate (mean +/ s.d. for continuous outcome, frequency/percentage for categorical variable): An estimated 10% of TKR patients will develop persistent postoperative pain (defined as NRS pain ≥ 4 with activity in the operated joint at 6 months postoperatively) 	
	 Number of groups being compared (use 1 for paired analysis within the same subjects): 1 	
	Effect size or change expected between groups: It is estimated that a onestandard deviation increase (an estimated 2.6 pg/ml [1]) in intraoperative joint fluid TNF-alpha level will be associated with 2.49 times the odds of developing persistent postoperative pain.	
	 Resulting number per group: Estimating an R 2 of 0.3 if TNFalpha were regressed on model covariates (i.e., model covariates would explain 30% of the variability in TNFalpha level), a total of 150 patients will need to be enrolled to detect an odds ratio of 2.49. 	
	Total sample size required: To account for 10% postoperative exclusions, we will enroll a total of 165 patients. 179 patients enrolled	

1.0 INTRODUCTION

The primary condition being studied is persistent pain following total knee arthroplasty (TKA) performed for knee osteoarthritis (OA). Published literature suggests that persistent postarthroplasty pain occurs in 1040% and joint stiffness requiring intervention occurs in 1040% of such patients and can adversely impact function and quality of life. This study is designed to test whether there is an association between joint fluid TNFalpha levels and development of persistent postoperative pain. The secondary condition being studied is joint stiffness following TKA performed for OA. Persistent pain can interfere with participation in physical therapy and may predispose patients to joint stiffness. Reciprocally, inflammation contributing to joint fibrosis and stiffness may also cause persistent postoperative pain. This study has the potential to shed light on the interaction between clinical, demographic and biological factors contributing to persistent postarthroplasty pain and joint stiffness in patients with knee OA.

Approximately 4 million Americans have undergone total knee arthroplasty (Weinstein AM et al., Estimating the burden of total knee replacement in the United States. J Bone Joint Surg Am 2013;95:38592), and persistent postoperative pain and joint stiffness may cause significant morbidity in up to 40% of these patients. This project aims to identify inflammatory pathways that contribute to and predict development of these complications. Identification of such pathways may allow us to target preventative measures to the patients at highest risk of persistent postoperative pain and joint stiffness.

[figure not shown]
While little is known about the contributions of inflammation and oxidative stress to the pathology of OA, even less is known about their contribution to adverse outcomes after arthroplasty. This study aims to define the incidence and characteristics of persistent postoperative pain and joint stiffness after TKA in patients with severe OA. This study also aims to explore demographic and medical factors as well as inflammatory pathways associated with the development of persistent postoperative pain and joint stiffness. Persistent postoperative pain may occur in as many as 2040% of patients (1), and clinical risk factors may include severity of preoperative pain (2), severe early postoperative pain and psychological factors, such as depression, anxiety, and pain catastrophizing (3). There is growing evidence that cytokines and adipokines are associated with OA severity, progression, and associated pain severity. Rodent studies have associated a number of cytokines, including tumor necrosis factor (TNF)alpha, interleukin (IL)1\(\beta\), IL6, IL10, nerve growth factor and calcitonin generelated peptide, to OAassociated pain syndromes, including inflammatory pain and central sensitization (4,5). IL1β and IL18 levels in joint fluid have been associated with OA severity and progression in humans (6), and serum IL15 levels have been shown to correlate with pain severity in patients with OA (7). In patients with knee OA, TNFalpha in synovial fluid is associated with total Western Ontario and McMaster Osteoarthritis Index (WOMAC) scores and each of its three subscales (8). In patients with OA scheduled to undergo knee arthroplasty, low levels of adiponectin, high levels of leptin, and low adiponectin/leptin ratios in synovial fluid have been associated with

increased preoperative pain severity. Finally, using the novel technology of mass cytometry, a recent study of total hip arthroplasty patients identified a correlation between specific signaling responses in CD14+ monocytes and rates of postoperative recovery of function and resolution of pain (9). Postoperative joint stiffness, which is defined as range of motion (ROM) ≤95 degrees (10), and persistent pain can cause significant morbidity following total knee arthroplasty (TKA). Clinically, risk of postoperative joint stiffness has been associated with factors such as preoperative ROM, younger age, nonwhite race, smoking, high cholesterol, improperly sized components, malalignment, retained osteophytes, and severity of postoperative pain (11,12,13). There is evidence of increased fibroblasts, T cells, mast cells, oxidative stress and activation of the TGFbeta pathway in arthrofibrotic tissue from patients who have undergone total knee arthroplasty (14,15,16). Information is lacking about which inflammatory pathways are active in the perioperative period that may cause persistent postoperative pain and joint stiffness and/or serve as predictors for those patients at highest risk of developing these complications. This study aims to help fill this knowledge gap using targeted tissue analysis as well as unbiased screening methods. By gathering longitudinal clinical data as well as blood, synovial fluid, and tissue samples from OA patients undergoing TKA, we can begin to elucidate risk factors for and inflammatory pathways contributing to persistent pain and/or stiffness compared to those who do not. While it is well known that deregulation of the immune response plays a major role in many autoimmune diseases like RA, the contribution of inflammation to the pathogenesis of OA, disarrayed postarthroplasty healing, and persistent postoperative pain has not been extensively explored. We hypothesize, based on prior studies noted above, that TNFalpha will be elevated in the synovial fluid of patients who develop persistent pain after TKA. In addition, we hypothesize that specific immune signatures predispose patients to develop persistent pain and joint stiffness. Using an unbiased informatics approach to survey complex pathways potentially contributing to adverse outcomes after TKA, we will perform cytokine protein arrays on joint fluid from all patients. In addition, a subset of 30 enrolled patients will be coenrolled as part of a control cohort for the rheumatoid arthritis FLARE study (IRB #13146). Blood and tissue from these patients will be prepared and stored to undergo cellbased analyses (flow cytometry and cytoF), histological examinations (immunohistochemistry), and RNA analysis (nanostring, reverse transcription polymerase chain reaction and RNAseq). Analysis of clinical and biological profiles from OA patients will enable us to better characterize risk factors for and inflammatory pathways contributing to persistent postoperative pain and restricted ROM after TKA. Ultimately, enhanced understanding of such associations has the potential to enable targeting of appropriate preventative interventions to those at highest risk of developing these complications.

2.0 OBJECTIVE(S) OF CLINICAL STUDY

This study is novel in taking a systematic approach to identifying and characterizing persistent pain and joint stiffness following TKA and analyzing activity of inflammatory pathways that may contribute to the development of these complications at a cellular and molecular level. This study has unique potential to fill in gaps in our understanding of how molecular and cellular pathology are associated with demographic factors, psychological factors, and medical comorbidities that contribute to postoperative pain and stiffness.

This study is designed to give us a better understanding of the inflammatory milieu associated with and potentially contributing to the development of persistent pain and/or joint stiffness after TKA. A better understanding of inflammatory contributors and clinical risk factors may allow us to recognize patients at high risk of these complications and may enable targeted interventions to reduce their incidence.

- 1. Determine if there is an association between preoperative joint fluid TNF-alpha, cytokine, chemokine, and adipokine levels and development of persistent postoperative pain and/or joint stiffness after TKA.
- 2. Determine if there is an association between preoperative plasma TNF-alpha, cytokine, chemokine, and adipokine levels and development of persistent postoperative pain and/or joint stiffness after TKA.
- 3. Determine the incidence, characteristics, and kinetics of persistent postoperative pain after TKA.
- 4. Determine the incidence, characteristics, and kinetics of postoperative joint stiffness after TKA.
- 5. Collect and store blood, joint fluid, and joint tissue for exploration of inflammatory signatures (identified by protein analyses, immunohistochemistry, RNA analysis including nanostring and sequencing analysis [RNAseq] and/or cellular analysis including flow cytometry and mass cytometry [cytoF]) associated with and potentially contributing to development of persistent postoperative pain and/or joint stiffness after TKA.
- 6. Collect clinical data for examination of interactions between demographic factors, comorbidities, pre- and post-operative pain, joint stiffness, inflammatory profiles, postoperative attainment of physical therapy (PT) goals, and functional outcomes after TKA.

3.0 STUDY HYPOTHESES

1. Elevated levels of TNF-alpha in joint fluid of patients with OA is associated with the risk of development of persistent postoperative pain after TKA.

- 2. Persistent pain (defined as NRS≥4 with activity in the operated joint at 6 months postoperatively) occurs in 10% of patients undergoing TKA for OA.
- 3. Joint stiffness (defined as range of motion [ROM] \leq 95 degrees measured at 6 \pm 2 weeks postoperatively) occurs in 7% of patients undergoing TKA for OA.
- 4. Distinct immune signatures (identified via protein analyses, immunohistochemistry, nanostring, RNA-Seq, fluorescence-activated cell sorting (FACS), and/or mass cytometry [CytoF]) are associated with the risk of developing persistent postoperative pain following TKA in OA patients.
- 5. Distinct immune signatures (identified via protein analyses, immunohistochemistry, nanostring, RNA-seq, FACS, and/or CytoF) are associated with the risk of developing joint stiffness following TKA.
- 6. Demographic profile, comorbidities, psychological factors, pain profiles, pre and postoperative stiffness and inflammatory profiles interact to determine attainment of PT goals and functional outcomes following TKA.

4.0 STUDY DESIGN

4.1 Endpoints

4.1.1 Primary Endpoint

• The presence of persistent pain (defined as NRS≥4 with activity in the operated joint) at 6 months postoperatively (measured at 6+ months).

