4.1.2 Secondary Endpoints

- 1. The incidence of postoperative joint stiffness (defined as ROM≤95 degrees) measured at the 6week (±2 weeks) postoperative surgical visit
- 2. Postoperative NRS pain scores measured on POD 1, POD 2, at 4 weeks, 3 months, and 6 months postoperatively
- 3. Postoperative knee ROM measured at 6 weeks (±2 weeks) postoperatively
- 4. Postoperative KOOS and PainDETECT (neuropathic pain assessment) scores measured at 4 weeks, 3 months, and 6 months postoperatively
- 5. Time to attainment of physical therapy goals (Ambulation 40 feet, independent transfer) measured during inpatient stay
- 6. New diagnoses and postoperative medications (recorded during hospital admission, during followup visits, and from postoperative phone followups and chart reviews)

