6.2 Postoperative Protocol

Pain and Function:

Depression, anxiety, pain at multiple sites, age, and sex have been shown to be associated with pain severity. Demographic information, psychological and medical history, and assessment of pain at multiple sites (using the Widespread Pain Inventory) will be collected or performed at enrollment. Because pain catastrophizing scale (PCS) scores are also associated with pain severity, the PCS will be administered on postoperative day (POD) 2. Furthermore, the following scales will be used to assess pain type and severity at enrollment and at 4 weeks (±3 days), 3 months (±1 week) and 6 months (±4 weeks) postoperatively. If patients initiate rescheduling of the postoperative phone calls, the surveys can be administered outside of the time window. If necessary, patients will be texted with their permission to schedule phone calls or surveys may be emailed to them via REDCap.

- 1. Numerical rating scale (NRS) pain scores (at rest, with movement, worst pain, least pain)
 - 2. The PainDETECT scale a validated measure of neuropathic pain
- 3. The KOOS questionnaire (Symptoms, Pain, Stiffness and Quality of Life subscales) and KOOS Physical Function Shortform a commonly utilized measure of pain and function in patients with knee OA NRS pain scores will also be collected on POD 1 and 2. Attainment of physical therapy goals will be recorded by research assistant on each inpatient day. In the OR, knee flexion and extension measurements will be made via visual assessments with the aid of a goniometer by the surgical team after anesthesia induction. At 6 months following enrollment, patients who developed postoperative joint stiffness and/or persistent chronic postoperative pain will be identified. Postoperative joint stiffness will be defined as ROM≤95 degrees at the 6week (±2 weeks) surgical followup in the postoperative clinic. Persistent postoperative pain will be defined as NRS≥4 with activity in the operated joint at 6 months postoperatively.

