6.3 Data Collection

[figure not shown]
The following data will be collected:

Pre-operative/Baseline

- Name
- MRN
- Age
- Race
- Ethnicity
- Gender
- Height
- Weight
- BMI
- Telephone number
- Email address
- Knee Extension (degrees)
- Knee flexion (degrees)
- History of depression
- History of anxiety
- History of diabetes
- History hyperlipidemia
- History of tobacco use
- Widespread pain inventory
- · Duration of preoperative opioid use
- Most recent intra-articular steroid injection in affected joint
- Statin use
- Gabapentinoid use
- Anticonvulsant use
- SSRI use
- Tricyclic antidepressant use
- SNRI use
- Presence of osteophytes on x-ray
- NRS pain score in operative knee at rest
- NRS pain score in operative knee with movement
- Worst NRS pain score in operative knee in past 24 hours
- Least NRS pain score in operative knee in past 24 hours
- PainDETECT questionnaire
- KOOS Knee survey
- Pain Questionnaire
- Quality of Life Questionnaire
- KOOS Physical Function Shortform

Surgical procedure (Intra-operative)

- Knee Extension (degrees)
- Knee flexion (degrees)
- Tourniquet time in OR

- Surgery start time
- Surgery end time
- Length of surgery
- Surgeon
- Anesthesiologist
- ASA
- Blood draw completed? (Y/N; Why)
- Blood draw arterial or venous?
- Blood drawn from side with IV? (Y/N; Why)
- Plasma aliquoted and stored? (Y/N)
- Blood hemolyzed (red plasma)? (Y/N)
- Joint fluid aspirated? (Y/N; Why)
- Did the joint fluid contain blood? (Y/N)
- Joint fluid aliquoted and stored? (Y/N)
- Was midazolam administered? (Y/N; dose)
- Was propofol administered? (Y/N)
- Was 4 mg dexamethasone administered intravenously? (Y/N)
- Was fentanyl administered? (Y/N; dose)
- Was ketorolac administered? (Y/N; dose)
- Was ketamine administered? (Y/N)
- Was dexmedetomidine administered? (Y/N)
- Did the patient receive neuraxial anesthesia with an epidural for postoperative pain? (Y/N)
- Did a patient receive an adductor canal/subsartorial saphenous nerve block containing ONLY local anesthetics (no additives)? (Y/N)
- Was topical TXA administered? (Y/N; dose)
- Was IV TXA administered either intraoperatively or postoperatively? (Y/N; dose)

Post-Operative

- Knee Extension (degrees)
- Knee flexion (degrees)
- Average daily opioid and non-opioid pain medication consumption
- Statin use
- Gabapentinoid use
- Anticonvulsant use
- SSRI use
- Tricyclic antidepressant use
- SNRI use
- NRS pain score in operative knee at rest
- NRS pain score in operative knee with movement

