7.0 STATISTICAL ANALYSIS

- Proposed analysis: Firth's penalized likelihood logistic regression
- Interim analysis planned: No
- Alpha level: 0.05
- Beta or power level: 0.8
- Primary outcome variable estimate (mean +/- s.d. for continuous outcome, frequency/percentage for categorical variable): An estimated 10% of TKR patients will develop persistent postoperative pain (defined as NRS pain ≥ 4 with activity in the operated joint at 6 months postoperatively)
- Number of groups being compared: 1
- Effect size or change expected between groups: It is estimated that a one-standard deviation increase (an estimated 2.6 pg/ml [1]) in intraoperative joint fluid TNFalpha level will be associated with 2.49 times the odds of developing persistent postoperative pain.
- Resulting number per group: Estimating an R 2 of 0.3 if TNFalpha were regressed on model covariates (i.e., model covariates would explain 30% of

the variability in TNFalpha level), a total of 150 patients will need to be enrolled to detect an odds ratio of 2.49.

 Total sample size required: To account for 10% postoperative exclusions, we will enroll a total of 165 patients. 179 patients enrolled

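### Do the two timings given for the 6-month pain score (sections 4.1.1 and 6.2) leave the primary endpoint undefined?

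*Combined protocol and SAP*

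**What the plan says.** Section 4.1.1 (Primary Endpoint) places persistent pain, an NRS of 4 or more with activity in the operated joint, "at 6 months postoperatively (measured at 6+ months").

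Section 6.2 (Postoperative Protocol) schedules the surveys that supply this score. The later ones fall at "3 months (±1 week) and 6 months (±4 weeks) postoperatively". It then relaxes the schedule: "If patients initiate rescheduling of the postoperative phone calls, the surveys can be administered outside of the time window". No limit in days is attached.

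The other places that define the endpoint give no window. Hypothesis 2 in section 3.0 reads "Persistent pain (defined as NRS≥4 with activity in the operated joint at 6 months postoperatively) occurs in 10% of patients undergoing TKA for OA". Section 7.0 says only "with activity in the operated joint at 6 months postoperatively". The secondary endpoints in 4.1.2 list "Postoperative NRS pain scores measured on POD 1, POD 2, at 4 weeks, 3 months, and 6 months postoperatively", again with no tolerance.

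Section 6.2 also says "At 6 months following enrollment, patients who developed postoperative joint stiffness and/or persistent chronic postoperative pain will be identified", which counts from enrollment, but the same paragraph goes on to define persistent pain by the score at 6 months after surgery.

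The source item is on the data list in 6.3: "NRS pain score in operative knee with movement".

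**The concern.** This is the only primary endpoint, and two sections appear to admit different interviews. The plus sign in 4.1.1, taken at face value, means not before 6 months and without an upper limit. Section 6.2 allows interviews up to four weeks early, and stops four weeks late unless the patient asked to reschedule. Section 7.0, where an analysis rule would be expected, is silent.

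If an analyst could pick either wording after seeing the data, a few patients might move in or out of an analysis that rests on about 15 or 16 cases. With so few events, an unwritten inclusion rule could in principle affect the odds ratio for TNF-alpha or the reported incidence.

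**Working it through.** **The plan's own figure.** Section 7.0 gives alpha 0.05, power 0.8, event rate 10%, odds ratio 2.49 per standard deviation and R² = 0.3. For logistic regression on one continuous predictor (Hsieh formula, two-sided):

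- n = (1.960 + 0.842)² / [0.10 × 0.90 × (ln 2.49)²] = 104.8
- Adjusted for covariates: 104.8 / (1 − 0.3) = 149.7, so 150, as stated.
- Exclusions: 150 × 1.10 = 165, as stated; 179 were enrolled.

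Interview timing is not an input, so 150 stands under either wording.

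**The window in days.** Six months = 365.25 / 2 = 182.6, taken as day 183 after surgery. Four weeks either side is day 155 to day 211, or 57 days.

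| Interview | 4.1.1 read literally | 6.2 |
|---|---|---|
| Days 155–182 (28 days, 28/57 = 49%) | no | yes |
| Days 183–211 (29 days, 51%) | yes | yes |
| After day 211, patient rescheduled | yes | yes |
| After day 211, not rescheduled by patient | yes | no |
| Before day 155, patient rescheduled | no | yes |

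The 49% is a share of permitted calendar days. It is not an estimate of the share of patients interviewed early; the documents give no interview dates.

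**Does any text remove an interview because of its date?** Section 5.3 lists no timing criterion. Section 6.1 names two grounds for removal around and after surgery: violations of the intraoperative anesthesia guidelines, at the investigator's discretion, and epidural PCA failure that requires IV PCA. Section 6.2 goes out of its way to keep surveys that miss the window. Section 7.0 has no exclusion on timing. So the default is that each patient's 6-month interview is used, whenever it was held.

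**Effect under that default.** Every row of the table is included. The patients, cases and model are the same whichever sentence is called the definition, so the change in n, power and incidence is zero. Neither the exact interview date nor a record of who asked to reschedule is needed.

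**Effect if 4.1.1 were enforced instead.** Assume the plan's 10% exclusions are the only loss.

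- Evaluable patients: 179 × 0.90 = 161; cases at 10%: 16.
- Incidence: 16/161 = 9.94%, exact 95% CI 5.8% to 15.6%.
- One case excluded: 15/160 = 9.38%, a shift of 0.56 percentage points; that case is 1/16 = 6.3% of all cases.
- Margin over the planned size: 161 − 150 = 11, so the twelfth exclusion (12/161 = 7.5%) takes n to 149.

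**The case for a change.** The best argument for a change is that a collection window is not an analysis rule. The plan never says that every score collected is analysed, and with about 16 cases even a small unwritten choice deserves to be closed before outcomes are linked to TNF-alpha. Section 6.1 has the samples assayed only once enrollment is complete, so there may be time, and a sentence costs little.

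Part of this stands. The wordings do differ, no other section reconciles them, and a written rule is better than an implied one. It does not amount to a needed change, because the rule one would write is the rule a competent analyst would already follow. Discarding a primary outcome that 6.2 expressly allowed to be collected would need a justification that the plan does not supply.

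A narrower rule, using only interviews that 6.2 permits, would be worse than the default. It would drop late interviews that 4.1.1 accepts, and it would need to know who initiated rescheduling, which the list in 6.3 does not include. An extra analysis limited to the window is a matter of preference; it would have fewer cases and could only be supportive.

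Two side points carry little weight. The wording about enrollment concerns when cases are identified, and the definition in the same paragraph counts from surgery. The absence of an interview date from 6.3 does not show that dates are not kept. It is also possible that the plus sign is a tolerance lost in text conversion, but the conclusion does not depend on that, and plus-minus signs do survive elsewhere in the text.

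**Conclusion.** The inconsistency is genuine but minor: loose wording in 4.1.1 against an operational schedule in 6.2. It calls for no change to the plan. If all 6-month interviews collected are analysed, which is the natural reading and the sound default, the effect on n, power and incidence is zero. Under strict enforcement of 4.1.1, which no passage prescribes, each excluded case would shift the incidence by about 0.6 percentage points, small beside an interval nearly 10 points wide, and 12 exclusions would be needed to fall below 150.

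This rests on two assumptions: that about 161 patients are evaluable (179 less the plan's 10%), and that the analyst does not discard interviews on timing. The number of early or late interviews is unknown, so the size of the strict-enforcement effect can be given only per excluded patient. Aligning the two sentences would be harmless tidying; it would alter no result.
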